### 4.2 PK SAMPLES COLLECTED OUTSIDE THE PK SAMPLING WINDOW DEFINED BY THE PROTOCOL

#### (1) Basic Definitions Related to the PK Sampling Window

Being outside the pre-specified PK sampling window is a common protocol deviation. This type of protocol deviation can be flagged or excluded, as discussed below.

Assuming three (3) adjacent PK sampling time points are  $t_{j-1}$ ,  $t_j$ , and  $t_{j+1}$  respectively, as demonstrated in **Figure 1** below.

The time gap of PK sampling time points  $t_j$  from the left and right sampling points  $t_{j-1}$  and  $t_{j+1}$  can be defined as follows by Eqs. (1) and (2), respectively.

$$g_j^- = t_j - t_{j-1} \quad (1)$$

$$g_j^+ = t_{j+1} - t_j \quad (2)$$

where,  $j = 1$  to 25, and  $t_1 = 0$ ,  $t_{25} = 600\text{min}$  (10hr).

For the last sampling point 720 min,  $g^+ = g^- = 720 - 600 = 120$  (min).

## (2) Criterion for Flag or Severe Protocol Deviation when Outside Sampling Window

In the case of a PK sample at time point  $j$  being collected outside the sampling window of  $t_j \pm w_j$ , a “flag-allowance” for the PK sample can be reasonably assigned to determine to flag or to exclude the corresponding PK sample, as follows:

The “flag allowance” for left ( $F^-$ ) and right ( $F^+$ ) sides, which are time intervals out of the specified sampling window, and are defined below, respectively:

[figure not shown]
$$F_j^\pm = \text{Max} \left( \frac{1}{2} g_j^\pm - w_j, 0 \right) \quad (3)$$

The flag allowance  $F^\pm$  is defined to avoid any overlapping between two adjacent PK sample timings. To be conservative, the final flag control, denoted as time intervals  $H^\pm$ , is defined as

$$H_j^\pm = \text{Min} (F_j^\pm, 2w_j) \quad (4)$$

Namely, the flag control cannot be more than two (2) times of the specified window.

**Figure 1. PK Sampling Points, Window and Flag Control**

Therefore, the maximum allowable out-of-window time, denoted as  $H_j^\pm$  can be obtained (see **Figure 1**). The proposed flag control of out-of-sampling-window for PK samples in this study are listed in **Table 4** below. Thus

- All PK samples outside the sampling window, but still within the final flag control are recorded as “flag” and “protocol deviation”, but not “severe protocol deviation”.
- All PK samples outside the final flag check are recorded as a “severe protocol deviation”.

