**Table 4. Flag Control of Out-of-Sampling-Window for I004-B PK Samples**

Sample Numbers	Sampling Plan					Time Range, min		Flag Allowance, min		Flag Control, min	
	tj, min	tj, hr	±	wj, min		g  /2	g + /2	F 	F +	H 	H +
C1	0										
C2	5		±	1	min	2.5	2.5	1.5	1.5	1.5	1.5
C3	10		±	1	min	2.5	5	1.5	4	1.5	2
C4	20		±	2	min	5	2.5	3	0.5	3	0.5
C5	25		±	2	min	2.5	2.5	0.5	0.5	0.5	0.5
C6	30		±	2	min	2.5	5	0.5	3	0.5	3
C7	40		±	3	min	5	5	2	2	2	2
C8	50		±	3	min	5	2.5	2	0	2	0
C9	55		±	3	min	2.5	2.5	0	0	0	0
C10	60		±	3	min	2.5	2.5	0	0	0	0
C11	65		±	3	min	2.5	2.5	0	0	0	0
C12	70		±	3	min	2.5	2.5	0	0	0	0
C13	75		±	3	min	2.5	2.5	0	0	0	0
C14	80		±	5	min	2.5	5	0	0	0	0
C15	90	1.5	±	5	min	5	7.5	0	2.5	0	2.5
C16	105	1.75	±	5	min	7.5	7.5	2.5	2.5	2.5	2.5
C17	120	2	±	5	min	7.5	15	2.5	10	2.5	10
C18	150	2.5	±	5	min	15	15	10	10	10	10
C19	180	3	±	10	min	15	15	5	5	5	5
C20	210	3.5	±	10	min	15	15	5	5	5	5
C21	240	4	±	10	min	15	30	5	20	5	20
C22	300	5	±	10	min	30	30	20	20	20	20
C23	360	6	±	10	min	30	60	20	50	20	20
C24	480	8	±	20	min	60	60	40	40	40	40
C25	600	10	±	20	min	60	60	40	40	40	40
C26	720	12	±	20	min	60	60	40	40	40	40

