## **6. STATISTICAL DESIGN AND ANALYSIS**

### **6.1 STUDY POPULATION**

#### **6.1.1 Evaluable Subjects and Per Protocol Population (PPP)**

##### **PPP-PK: Per-Protocol Population for PK Analysis**

The PPP-PK is defined as all subjects who have received both study drugs during the study and are evaluable for both treatments. Primary PK analyses will be performed based on the PPP-PK.

In order to be evaluable for the primary analyses of this study, a subject must meet all of the following six (6) criteria for both treatments:

- (1) Correct dose and administration for both T and R treatments.
- (2) Nineteen (19) or more of 25 post-dose PK data (>75%) for serum concentration points are available;
- (3) There are no more than four (4) consecutive missing PK data points;
- (4) The baseline PK data point and the 12-hour post-dose PK data are available;
- (5) At least five (5) of the seven (7) PK data points at 50, 55, 60, 65, 70, 75, and 80, post-dose are available;
- (6) At least three (3) of the PK data points at 5, 6, 8, and 10 hours post-dose are available.

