## **6.2 MISSING DATA HANDLING**

### **6.2.1 Missing Data Handling for Evaluable Subjects**

For an evaluable subject that was defined in Section 6.1.1, only a small portion of PK measurements, if any, are allowed to be missed, and the interpolation method will be used for imputation.

If the PK data at t=12 hrs is missed, the exploration method is allowed.

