### 6.3.2 Severe Protocol Deviation Assessed by Management Review Board

The Management Review Board (MRB) may determine that some data should be excluded from PPP analysis due to severe protocol deviation (SPD). SPD include, but are not limited to,

- Full dose of study drug not administered (ICH category III);
- Use of prohibited drugs (ICH category IV);
- Violating drug, alcohol, or caffeine restriction;
- Sample handling (extreme deviations of sample isolation time, centrifuge time, sampling record etc.); and
- Severe out of the sampling window time (see **Section 5.6.3**).

The data for excluded samples due to SPD will be considered missing data (see **Section 5.2**).

Thus, two datasets will exist for

- SPD-excluded (SPD-E) dataset: identified SPD data are excluded and are considered as missing data;
- SPD-included (SPD-I) dataset: identified all SPD data are still used in the data analysis.

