**Table 5. Datasets for I004-B: PK Evaluation**

Factors to Determine Datasets			Laboratory PK Data Analysis	
			Initially-Tested Data (ITD)	Final Reported Data (FRD)
Assessment for Severe Protocol Deviation (SPD)	No SPD Observed	-	ITD	FRD
	SPD Observed	SPD-excluded (SPD-E)	ITD + SPD-E	FRD + SPD-E
		SPD-included (SPD-I)	ITD + SPD-I	FRD + SPD-I

The PK BE statistical analysis will be conducted for all four (4) datasets (**Table 5**). Among the datasets, the final reported data for SPD-excluded (FRD + SPD-E) dataset is the most reasonable one and should be considered as the formal results for PK evaluation.

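### Around the expected peak, Table 4 leaves no flag-only zone, so PK draws only minutes off schedule are labelled severe deviations and, if the review board agrees, replaced by interpolation in the formal dataset although their times are known

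*SAP*

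**What the plan says.** SAP 4.2 gives each PK sample a window w and, beyond it, a flag control H. A sample outside w but within H is flagged and kept. Beyond that, "All PK samples outside the final flag check are recorded as a" severe protocol deviation (SPD). The values of H are in Table 4, "Flag Control of Out-of-Sampling-Window for I004-B PK Samples".

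The consequences are spread over several sections:

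- SAP 6.3.2 lists severe out-of-window timing as an SPD and says that the MRB may decide to exclude data on that ground. It adds: "The data for excluded samples due to SPD will be considered missing data".
- SAP 6.2.1 says that for missing PK points "the interpolation method will be used for imputation".
- SAP 6.3.3 analyses four PK datasets. The final reported data with SPDs excluded (FRD + SPD-E) "should be considered as the formal results for PK evaluation".
- SAP 6.1.1, PPP-PK criterion (5), requires for both treatments: "At least five (5) of the seven (7) PK data points at 50, 55, 60, 65, 70, 75, and 80, post-dose are available".

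SAP 5.1 computes AUC from the sampling time without saying whether that is the actual or the nominal time.

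**The concern.** A sample can be judged out of window only if its collection time is on record. For a timing deviation alone, the formal analysis may therefore discard a measured concentration at a known time and put an interpolated value in its place. The affected points are those sampled most densely, evidently to capture the peak, and Cmax is a primary endpoint. They also count toward evaluability, so a short run of late draws in one period can remove a subject from the formal PK comparison for both treatments.

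The decision to exclude is left to a board with no criterion for when a late sample stays in. That is discretion over a primary endpoint, and a plan can remove it at little cost.

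**Working it through.** **Inputs.** Nominal times, w and H are from SAP Table 4; the formulas are SAP Eqs. (1)-(4); the five-of-seven rule is SAP 6.1.1; the half-life of 81 min is from Protocol 4.2. Lateness rates, tmax and assay noise are assumptions, because the documents give none.

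**Step 1: reproduce Table 4.** With g the gap to the neighbouring nominal time, F = max(g/2 − w, 0) and H = min(F, 2w). On the cap, the SAP says: "Namely, the flag control cannot be more than two (2) times of the specified window". The limit before a sample becomes an SPD is w + H. All 25 post-dose pairs of H in Table 4 reproduce. The rows that matter here, as early/late values in minutes:

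| Nominal time | w | g/2 | H | Limit |
|---|---|---|---|---|
| 50 min | 3 | 5 / 2.5 | 2 / 0 | 5 / 3 |
| 55, 60, 65, 70, 75 min | 3 | 2.5 / 2.5 | 0 / 0 | 3 / 3 |
| 80 min | 5 | 2.5 / 5 | 0 / 0 | 5 / 5 |
| 720 min | 20 | 60 / 60 | 40 / 40 | 60 / 60 |

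A 55-min sample drawn at 59 min is an SPD. A 12-hour sample drawn 60 min off is only flagged. The cause is Eq. (3): the denser the sampling, the smaller the allowance.

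**Step 2: criterion (5).** Three or more of the seven draws lost in one period leave at most four, so the subject fails. There are five possible runs of three consecutive draws. If each draw is 4 min late, the runs 50/55/60, 55/60/65, 60/65/70 and 65/70/75 each produce three SPDs. The run 70/75/80 produces only two, because 80 min tolerates 5 min; five of seven then remain and the subject stays evaluable.

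**Step 3: size of the loss.** Let p be the assumed independent probability that a draw at 50 to 80 min is an SPD and is excluded. Per period, q = P(at least 3 of 7) = 1 − (1−p)^7 − 7p(1−p)^6 − 21p²(1−p)^5. Over two periods the subject is lost with probability 1 − (1−q)². Expected excluded draws are 60 × 2 × 7 × p = 840p.

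| p | q | Subjects lost | Of 60 | Draws excluded, of 840 |
|---|---|---|---|---|
| 2% | 0.0003 | 0.05% | 0.03 | 16.8 |
| 5% | 0.0038 | 0.75% | 0.45 | 42 |
| 10% | 0.0257 | 5.1% | 3.0 | 84 |
| 15% | 0.0738 | 14.2% | 8.5 | 126 |

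This gives the 80-min draw the same p as the others although its limit is wider, and it ignores clustering of late draws within a visit.

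**Step 4: effect on the endpoints.** A one-compartment profile was simulated with half-life 81 min and assumed tmax 60 min; two of the 55 to 75 min samples were drawn 4 min late and then deleted. Mean Cmax falls by about 0.06% with no assay noise and by 1.3% to 1.4% with an assumed 8% noise. Mean AUC(0-12h) changes by about 0.01%. Most of the Cmax change is an effect of noise: with 8% noise the observed maximum overshoots the noise-free peak by about 10.4% before deletion and 8.9% after it.

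**The case against.** Much of the case for the plan stands.

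- **Exclusion is not automatic.** The SPD label is, but SAP 4.2 says that such samples can be flagged or excluded, and 6.3.2 says that the MRB may exclude them. This softens the rule but leaves the decision without a criterion.
- **The alternative analysis is already planned.** A reader might infer that off-time samples vanish from every analysis. They do not: the SPD-included dataset keeps them and is analysed, though not as the formal result.
- **Not every late run removes a subject.** It is tempting to say that any three consecutive peak draws 4 min late do so; 70/75/80 min does not.
- **Overlap.** A reader might say that the flag allowance fails its own purpose, since it "is defined to avoid any overlapping between two adjacent PK sample timings" and permitted windows already overlap (55 + 3 = 58 is later than 60 − 3 = 57). That overlap comes from the protocol's windows in Table 7-2. The allowance is zero there and adds none.
- **T/R ratio.** A reader might infer bias in the equivalence result. The rule is the same for both treatments, and Protocol 6.6 blinds study staff and laboratory analysts. No bias, change in interval width or loss of power has been demonstrated.
- **Frequency and replacement.** No lateness rate is documented. Protocol Appendix B stresses correct timing, 7.15 allows other sampling sites, and the synopsis enrols until 60 subjects are evaluable. This limits the loss in numbers but does not recover discarded measurements.
- **Actual time.** SAP 5.1 may already mean actual times, and it calls tmax an observed value. That is a natural reading, but it is not stated.

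**Conclusion.** The point holds as a fault in the formal dataset rule. Read together, SAP 4.2, 6.2.1, 6.3.2 and 6.3.3 allow a valid concentration at a known time to be replaced by an interpolated one for an offset of more than 3 min (5 min at 80 min; late side only at 50 min), while far larger offsets later in the profile are kept. The cost is lost valid data, lost evaluable subjects and unguided discretion over a primary endpoint.

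The loss of subjects is negligible at an assumed 2% rate and material at 10% or more; the true rate cannot be known from the documents. The Cmax effect is small and rests mainly on the assumed noise. The change is worth making before unblinding because it is cheap, not because the equivalence conclusion has been shown to be at risk.

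**What to change.** - **SAP 5.1:** state that Eqs. (14)-(15) and tmax use actual elapsed sampling times.
- **SAP 4.2 and 6.3.2:** use Table 4 for flagging and listing only. Keep every sample with a reliable recorded time in the formal dataset at that time.
- **SAP 6.3.2:** reserve exclusion for samples with no reliable time or with compromised handling. Correct the cross-references, which point to Sections 5.6.3 and 5.2 although the rules are in 4.2 and 6.2.
- **SAP 6.3.3:** report the version that excludes samples for timing as a sensitivity analysis.

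The cost is SAP wording and programming only. Actual times must be carried into the PK program, and a few irregularly timed points will enter the profiles.

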**Table 4. Flag Control of Out-of-Sampling-Window for I004-B PK Samples**

Sample Numbers	Sampling Plan					Time Range, min		Flag Allowance, min		Flag Control, min	
	tj, min	tj, hr	±	wj, min		g  /2	g + /2	F 	F +	H 	H +
C1	0										
C2	5		±	1	min	2.5	2.5	1.5	1.5	1.5	1.5
C3	10		±	1	min	2.5	5	1.5	4	1.5	2
C4	20		±	2	min	5	2.5	3	0.5	3	0.5
C5	25		±	2	min	2.5	2.5	0.5	0.5	0.5	0.5
C6	30		±	2	min	2.5	5	0.5	3	0.5	3
C7	40		±	3	min	5	5	2	2	2	2
C8	50		±	3	min	5	2.5	2	0	2	0
C9	55		±	3	min	2.5	2.5	0	0	0	0
C10	60		±	3	min	2.5	2.5	0	0	0	0
C11	65		±	3	min	2.5	2.5	0	0	0	0
C12	70		±	3	min	2.5	2.5	0	0	0	0
C13	75		±	3	min	2.5	2.5	0	0	0	0
C14	80		±	5	min	2.5	5	0	0	0	0
C15	90	1.5	±	5	min	5	7.5	0	2.5	0	2.5
C16	105	1.75	±	5	min	7.5	7.5	2.5	2.5	2.5	2.5
C17	120	2	±	5	min	7.5	15	2.5	10	2.5	10
C18	150	2.5	±	5	min	15	15	10	10	10	10
C19	180	3	±	10	min	15	15	5	5	5	5
C20	210	3.5	±	10	min	15	15	5	5	5	5
C21	240	4	±	10	min	15	30	5	20	5	20
C22	300	5	±	10	min	30	30	20	20	20	20
C23	360	6	±	10	min	30	60	20	50	20	20
C24	480	8	±	20	min	60	60	40	40	40	40
C25	600	10	±	20	min	60	60	40	40	40	40
C26	720	12	±	20	min	60	60	40	40	40	40

### 4.3 QUALITY OF PD CLAMP DATA

At each study visit, the PD GIR required to maintain blood glucose at the target level ( $\pm 10\%$ ) by clamp technology is recorded every minute for 12 hours. The target level is “baseline -5 mg/dL”. The baseline is defined as the average of the available three (3) glucose levels at -30

min, -20 min and -10 min time measure by YSI 2300 STAT Glucose Analyzer for the subject at the treatment. If one or two of these three (3) glucose levels are missed. The data should be flagged.

#### 4.3.1 Precision of Clamp Data

The precision is reported as CV (coefficient of variance) of device blood sugar. For a given subject  $i$  in a given treatment  $X$  ( $X=T$  or  $R$ ) at a given time point  $t$ , the blood glucose (BG) level is denoted as  $g_{i,X}(t)$ , and the average of BG is obtained as

$$G_{i,X} = \frac{1}{n_t} \sum_t g_{i,X}(t) \quad (5)$$

Calculations for CV by Eq. (5) is based on each clamp from the minute that the glucose infusion rate is initiated (Start of GIRa) to the minute that the glucose infusion rate is no longer required (End of GIRb) or at the end of the clamp at the 12-hour mark, whichever appears first. Note that an End of GIR is not necessarily an end of the clamp. In Eq. (5),  $n_t$  is total number of GIR data for the subject in the treatment per the above calculation method.

The precision for the clamp data point, denoted as  $p_{i,X}$ , can be measured using the coefficient of variance (CV, in %) as defined below:

$$p_{i,X} = \frac{\sigma_{i,X}}{G_{i,X}} \times 100\% \quad (6)$$

where  $\sigma_{i,X}$  is the standard deviation of the BG data of  $g_{i,X}(t)$ . It is expected that  $p_{i,X} < 12\%$ .

For the subjects with clamp precision  $\geq 10\%$ , the data should be flagged and tabulated. If  $p_{i,X} \geq 12\%$ , the clamp data for the treatment of the subject should be rejected.

The clamp precision for a given treatment  $X$ , is then calculated as

---

a **Start of GIR:** After dosing of Insulin Aspart, the onset of insulin action was identified by a decline of 5mg/dL or more for glucose concentration from the baseline level, the corresponding onset time is denoted as  $t_{\text{onset}}$ . At or after  $t_{\text{onset}}$ , the first time point with  $\text{GIR}(t) > 0$ , is the start of GIR.

b **End of GIR:** If the last time point with  $\text{GIR}(t_{\text{last}}) > 0$ , then starting from  $t = t_{\text{last}} + 1$ , the glucose infusion rate is no longer required, the time for end of GIR is  $\text{Min}(t_{\text{last}} + 1, 720)$ .

$$P_X = \frac{1}{n_X} \sum_{i=1}^{n_X} p_{i,X} \quad (7)$$

where  $n_X$  is the number of subjects in the treatment X.

#### 4.3.2 Deviation from Target (DFT)

The clinical protocol required that “the individual blood glucose clamp target level will be determined for each subject by the mean fasting glucose level minus 5 mg/dL.”, which can be defined as  $g_0$ .

The baseline of blood glucose is the mean fasting glucose level from three (3) results measured by YSI 2300 STAT Glucose Analyzer at -30min, -20min, and -10min.

The actual blood glucose level for each corresponding clamp data point is denoted as  $g_{i,X}(t)$ . The average deviation from the target (DFT) for a given subject  $i$  in treatment  $X$  is then defined as

$$d_{i,X} = \frac{1}{n_t} \sum_t \frac{g_{i,X}(t) - g_0}{g_0} \times 100\% \quad (8)$$

In calculation DFT (Eq. (9)), the time  $t$  runs the same as that for Eq. (5). It is also expected  $d_{i,X} < 12\%$ . For the subjects with  $DFT \geq 10\%$ , the data should be flagged and tabulated. If  $d_{i,X} \geq 12\%$ , the clamp data should be rejected.

The DFT for a treatment  $X$  is obtained by the following calculation:

$$D_X = \frac{1}{n_X} \sum_{i=1}^{n_X} d_{i,X} \quad (9)$$

where  $n_X$  is the number of subjects in the treatment X.

#### 4.3.3 Accuracy

Accuracy (denoted as  $A$ ) is defined as mean difference of all paired BG measurements of device vs reference method represented as a percentage.

$$A = \frac{1}{n'_t} \sum_t \left( \frac{g_{i,X}(t) - g'_{i,X}(t)}{g'_{i,X}(t)} \times 100\% \right) \quad (10)$$

where  $g^{i,X}$  is the BG measured by Biostator,  
 $g'_{i,X}$  is the BG measured by YSI Glucose analyzer,  
 $t$  is the time point when BG measurement by both methods are available, and  $t$  runs through all such both method data available time points;  
 $n'_t$  is number of time points with BG measurement by both Biostator and YSI Glucose analyzer.

#### 4.4 SMOOTHING OF PD DATA

During the 12-hour study, GIR PD data were collected every minute for each treatment (T or R) of each subject using clamp technique. In fact, 721 PD data points (0-720 min) were measured for each treatment (T or R) of each subject.

Due to the nature of the clamp technique, the PD data are highly fluctuating as a function of time, so smoothing is required before calculating PD parameters (such as  $GIR_{max}$ ,  $AUC_{GIR}$ , etc.). The smoothing procedure has been designed to accommodate data for which

$$y_i = k(t_i) + \varepsilon_i \quad (11)$$

where  $y_i$  is the actual PD observation as GIR at time  $i$ ,  $k$  is a smooth function of PD, and the  $\varepsilon_i$  are random variables with mean 0 and constant scale,  $\varepsilon_i \in (0, \sigma^2)$ . Within such a framework,  $\hat{y}_i$  is an estimate of  $k(t_i)$ . The assumption of smoothness allows points in a neighborhood of  $(t_i, y_i)$  to be used to form  $\hat{y}_i$ .

For the actual smoothing, the SAS standard program Locally Estimated Scatterplot Smoothing (LOESS) in SAS/STAT 13.1 is used.

The LOESS method uses weighted least squares to fit linear or quadratic functions of the predictors to the centers of the neighborhoods. The radius of each neighborhood is chosen so that the neighborhood contains a specified percentage of the data points. The fraction of the data, called the smoothing parameter, in each local neighborhood controls the smoothness of the estimated surface. Data points in a given local neighborhood are weighted by a smooth decreasing function of their distance from the center of the neighborhood. Therefore,

$$M = s N \quad (12)$$

where, N is the total number of experimental data points. For PD data of this study, N=721.

M is the number of data points in a given local neighborhood, and  
s is the smoothing parameter, specifying a fraction of the total PD data.

This SAP suggests using smoothing parameter  $s=0.0125$ , so that M=9, namely there are 9 data points in each neighborhood.

## 5. CALCULATION OF RELATED STATISTICAL QUANTITIES

### 5.1 PK PARAMETERS

#### 5.1.1 Primary Endpoints and Related Quantities

- (1)  $C_{max}$ , in units of pg/mL, is defined as the maximum of observed serum Insulin Aspart (IA) concentration for a given subject and given treatment over all PK sample concentrations:

$$C_{max} = \max(C_1, \dots, C_i, \dots, C_n) \quad i = 1, 2, 3 \dots n \quad (13)$$

where  $n=26$ , and  $C_i$  is rounded to 10% of the quantitative limit (QL) of the validated test method for IA.

- (2)  $AUC_{IA(0-12h)}$ , in units of pg/mL\*hr, can be calculated per the trapezoidal rule and sampling time for each treatment of each subject as given the Eq. (14):

$$AUC_{0-12h} = \sum_{i=1}^{n-1} \frac{C_i + C_{i+1}}{2} (t_{i+1} - t_i) \quad (14)$$

where  $n$  is the number of available PK measurements,

$t_1$  is the baseline, and

$t_n$  is the sampling time for the last scheduled PK measurement,  $t_n = 12 \text{ hours}$ .

#### 5.1.2 Secondary Endpoints

- (1)  $t_{max}$  is an observed value, corresponding when  $C_{max}$  appears, and is represented in units of “minutes”, or “min”.
- (2) Partial  $AUC_{IA(t_{m1}-t_{m2})}$ , in units of pg/mL\*hr, can be calculated per the trapezoidal rule and sampling time for each treatment of each subject similarly as the Eq. (14):

$$AUC_{t_{m1}-t_{m2}} = \sum_{i=m_1}^{m_2-1} \frac{C_i + C_{i+1}}{2} (t_{i+1} - t_i) \quad (15)$$

where,  $t_{m1}$  and  $t_{m2}$  are the starting and ending sampling times of PK measurement for the partial  $AUC_{IA(t_{m1}-t_{m2})}$ , respectively;

$m$  is the number of available PK measurements.

The following partial AUC of Insulin Aspart will be calculated: (i)  $AUC_{IA(0-1h)}$ , (ii)  $AUC_{IA(0-2h)}$ , (iii)  $AUC_{IA(0-4h)}$ , and (iv)  $AUC_{IA(4-12h)}$ .

(3)  $AUC_{IA(0-\infty)}$ , in units of pg/mL\*hr, is defined as  $AUC_{0-t^*}$ , with  $t^* > t$  and meets

$$C(t^*) = C_1, \text{ if } C(t) > \max(C_1, QL) \quad (16)$$

where  $C_1$  = baseline, and  $t=12$  hrs, the time point for the last sample collection ;  
 QL is the analytical method's quantitation limit (QL)

When  $C(t) \leq \max(C_1, QL)$ ,

$$AUC_{0-\infty} = AUC_{0-t} \quad (17)$$

Otherwise

$$AUC_{0-\infty} = AUC_{0-t} + AUC_{t-\infty} \quad (18)$$

$AUC_{0-t}$  can be calculated per the trapezoidal rule as given in the Eq. (14).  $AUC_{t-\infty}$  can be obtained per the extrapolation method as given in the Eq. (19) below, based on

$$AUC_{t-\infty} = \int_{t_n}^{\infty} C(t)dt \approx -\frac{1}{K_e} B e^{-k_e t} \Big|_{t_n}^{\infty} = \frac{C_n - C_1}{K_e} \quad (19)$$

where  $C_n = C(t_n)$  is the last available PK measurement for serum IA concentration;  
 $K_e$  is the rate constant of elimination obtained per the method described in the next paragraph; and  
 $B$  is a constant, irrelevant to time.

If the  $AUC_{t-\infty}$  (Eq. (18)) cannot be found as a converged data for a subject, specifically:

- A positive  $K_e$  cannot be found; or
- The obtained  $AUC_{t-\infty}$  is much larger than 30% of  $AUC_{0-t}$ ;

then, the data of  $AUC_{0-\infty}$  for the treatment of the subject can be considered as not available.

(4) The Elimination Rate Constant,  $K_e$ , by Least Square Model

$K_e$  will be obtained by the software output. In case the software cannot report the data of  $K_e$ , then  $K_e$  is calculated based on the least squares model from the logarithm of the last three (3)

or more ( $m=3, 4, 5, 6$ ) available PK measurements of the treatment for the subject, per the following linear equation:

$$\ln [C(t)] = a + pt \quad (20)$$

where  $p$  is the slope, and  $a$  is the intercept irrelevant to time, and  $K_e = -p$ .

A converged  $p_m$  can be accepted as the final  $p$ , for which the coefficient of variance (CV) of  $p_m$  and  $p_{m+1}$  is not more than 20%. When  $m$  is up to 6 and  $CV \leq 20\%$  is not achieved, the  $p_m$  with lowest CV with  $p_{m+1}$  will be used as the final  $p$ .

Here,  $m$  is the number of serum samples used to calculate  $K_e$ , where  $K_e = -p$ .

If there is no convergence of  $p$  or  $K_e$  that can be obtained, the corresponding data of  $AUC_{0-\infty}$  for the subject is considered “not available”.

$K_e$  will not be included in tables or listings, but is referred to in the definitions of other PK parameters.

(5) Apparent clearance (CL/F), in units of L/hr, can be computed as:

$$CL/F = \frac{Dose}{AUC_{0-\infty}} \quad (21)$$

(6) Apparent volume of distribution ( $V_z/F$ ), in units of L, can be calculated as:

$$V_z/F = \frac{CL/F}{K_e} \quad (22)$$

(7) Half-life ( $t_{1/2}$ ) is defined as the time required for the drug concentration to decrease by a factor of one-half in terminal phase, and it can be estimated as:

$$t_{1/2} = \frac{\ln(2)}{K_e} \quad (23)$$

Half-life is reported in units of hr.

